Study Protocol, NCT 03604497

(last updated 8/16/19)

Beacon Study Protocol

I. Consent

There are two ways for participants to complete consent. Participants who scheduled an appointment are given the option to complete the consent and questionnaires before they come download the app. If they indicate they have done this method, **you must check on Qualtrics and make sure that they have completed this step before downloading the app on their phones.** If they have completed the consent and questionnaires, inform them about how the app functions and the purpose of the study and answer any questions they have.

Alternatively, we can complete consent in lab. Consent will be done using the iPads in lab if the participant is a walk-in appointment or if they did not complete consent before their appointment. Click on the “Beacon Consent” app on the iPads to continue. Enter the participant ID into the survey, which can be found on the “Beacon Participant List” Excel spreadsheet in the Shares Drive inside the “BEACON” Folder. Select the first available ID number.

Explain the consent form briefly to participants, allow them to read the consent for and answer any questions. Inform them about how the app functions and the purpose of the study. If they select “Agree”, you may proceed.

II. Questionnaires

For participants who have not yet completed questionnaires, they should be completed in the waiting room on the iPads following completion of the consent process. Complete:

- Walking Journal
- Cell phone usage survey
- Demographics sheet

Collect iPads once participants have completed the survey.

III. Download App

Participants who have finished the consent process and the surveys can bring their phones back for download. Ideally, while one researcher works with participants to download the app, another researcher can have participants fill out the W-9 form and process the payment.

IV. Payment

Have participants complete W-9 form for payment. Greenphire will be used to process each participant's payment. Anyone with access to the Greenphire login can upload the participant's information to Greenphire. Log in from <https://www.clincard.com/login/>. Click on "Register Subject" and select the study ending with "300001917". Enter in participants' Subject ID, first and last name, address, and date of birth. Click on "Register". Click on "Assign Card". Click on "Request Payment".

Tell participants to allow about 24 hours for payment to be approved. Thank them for coming in and remind them of the following:

1. They should not delete the app off their phone for the full Fall semester. We will be monitoring this remotely and ask them to return to lab if they delete the app.
2. They should cross the intersection of 14th and University at least 4 times a week, and ideally more often.
3. If they have an iPhone and their phone goes dead (e.g. dead battery) or is turned off for some reason, they need to re-start the app. If they don't do this, we will know it remotely and contact them to do it.
4. The app will not do anything for several weeks. At some point later in the semester, they will start getting alerts to remind them not to cross the street while distracted. We cannot tell them when these alerts will start, and it may be different for different people.

Data Analysis Plan, NCT 03604497

October 9, 2020

Data Analysis. Baseline characteristics were examined descriptively, and then primary analyses were conducted using general estimating equation logistic regressions to account for the dependence of crossing events within participants. The models estimated odds ratios (ORs) and associated 95% confidence intervals (CIs) for the association between the study intervention phase (i.e., pre-intervention, intervention, and post-intervention phases) and distraction (whether visual or aural). Models were adjusted for age, race, distraction prevalence during the pre-intervention phase, and type of phone (i.e., Android or iOS). Given potential for user curiosity at the start of each phase creating changed behavior, a sensitivity analysis was conducted by comparing behavior in the third week of each phase rather than behavior across the full phase.

Next, since anecdotal evidence suggested users were curious about how the alert functioned and therefore used their phone purposely as they approached the intersection, creating artificial datapoints, we conducted analyses stratified by extent of baseline distraction. Finally, we recognized the Android and iOS platforms offered very different alerts to pedestrians, so analyses were conducted to examine whether effect modification by both the prevalence of pre-intervention distraction and phone type was meaningful by including a three-way interaction of intervention phase, distraction category, and phone type in an age- and race-adjusted model examining stratified ORs.

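### Does adjusting for a noisy pre-intervention distraction prevalence leave the phase odds ratios open to a changing mix of pedestrians?

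*SAP*

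**What the plan says.** The first paragraph of the SAP's Data Analysis text gives the model: "primary analyses were conducted using general estimating equation logistic regressions to account for the dependence of crossing events within participants". The association of interest is between "study intervention phase (i.e., pre-intervention, intervention, and post-intervention phases) and distraction (whether visual or aural"), and the adjustment set is given in one sentence: "Models were adjusted for age, race, distraction prevalence during the pre-intervention phase, and type of phone (i.e., Android or iOS"). The working correlation is not stated.

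Two further analyses bear on the point. One is a sensitivity analysis "comparing behavior in the third week of each phase rather than behavior across the full phase". The other, in the second paragraph, is described thus: "we conducted analyses stratified by extent of baseline distraction". The SAP motivates both by users' curiosity about the app or its alert.

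The protocol's reminders in section IV (Payment) govern how many crossings each person contributes. Participants are asked to cross "at least 4 times a week, and ideally more often". On retention, "They should not delete the app off their phone for the full Fall semester", and "We will be monitoring this remotely and ask them to return to lab if they delete the app". Reminder 3 adds that an iPhone app left unstarted after a shutdown is detected remotely and the participant contacted.

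**The concern.** The question is whether the same people behave differently once alerts begin, yet the unit of analysis is the crossing. The protocol sets a floor on crossings and no ceiling, and it foresees deleted apps and phones that stop recording. So the share of crossings supplied by habitually distracted people could differ between phases.

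An analyst would expect the baseline covariate to deal with this. But it is computed from outcomes in the reference phase, over a finite count, so it is an error-prone stand-in for tendency, and adjusting for it corrects only partly. Whatever remains would look like an effect of the alert. Neither the third-week analysis nor the baseline strata hold the participant fixed, so neither would expose it. With a small reported effect, a few percent on the odds ratio could matter.

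**Working it through.** The documents give no sample size, prevalence, effect size or crossing total, so there is no planned figure to reproduce. The size of the bias has to be simulated under stated assumptions.

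**From the documents.** At least 4 crossings a week are requested. A third-week analysis implies phases of at least 3 weeks. Hence 4 × 3 = 12 crossings per phase, at the requested minimum and the shortest phase length.

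**Assumed.** Each person has a stable logit-normal tendency to be distracted. Later-phase crossings are multiplied by exp(g) per SD of tendency. A mild shift is g = ±0.2, that is ×1.22 or ×0.82. A strong shift in the second set below is ×1.5 or ×0.67.

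**First set:** 60,000 participants per scenario, median prevalence 30%, SD 1.5 on the logit scale, true odds ratio 1, intervention versus pre-intervention.

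| Crossings per phase | Shift per SD | Unadjusted, independence | Adjusted, independence | Adjusted, exchangeable | Stratified by participant |
|---|---|---|---|---|---|
| 12 | none | 0.995 | 0.989 | 0.990 | 0.991 |
| 12 | ×1.22 | 1.240 | 1.038 | 1.017 | 0.999 |
| 12 | ×0.82 | 0.805 | 0.958 | 0.979 | 1.000 |
| 24 | ×1.22 | 1.238 | 1.022 | 1.008 | 0.998 |
| 24 | ×0.82 | 0.803 | 0.974 | 0.988 | 0.999 |
| 4 | ×1.22 | 1.239 | 1.092 | 1.047 | 1.007 |
| 4 | ×0.82 | 0.805 | 0.904 | 0.947 | 1.003 |

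Share of the log-odds-ratio bias removed by the planned covariate at 12 crossings, under independence:
- upward shift: 1 − ln(1.038)/ln(1.240) = 1 − 0.0373/0.2151 = 83%;
- downward shift: 1 − ln(0.958)/ln(0.805) = 1 − 0.0429/0.2169 = 80%.

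Across all 12-crossing scenarios, adjusting for true tendency gave 0.99–1.01. The remainder therefore comes from noise in the observed prevalence.

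**Second set:** prevalence 0.3, ICC 0.3, 12 crossings.
- Two phases, independence: 0.96–0.97 and 1.03 (mild), 0.93 and 1.07 (strong).
- Three phases in one model, independence: 0.95 and 1.04 (mild), 0.91 and 1.09 (strong).
- Exchangeable: 0.98 and 1.02 (mild), 0.95 and 1.05 (strong).
- 48 crossings, three phases, mild: 0.98 and 1.02.
- App deletion by 25% of the more distracted half against 10% of the rest: 0.98; 40% against 10%: 0.96.

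**With a real effect** (true odds ratio 0.70, first-set assumptions, 12 crossings, independence): 0.70 with no shift, 0.74 or 0.68 with a mild one. The stratified odds ratio was 0.70–0.71.

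**Would the extra check settle it?** Suppose later crossings fall with the prevalence a person happened to show in the pre-intervention phase, rather than with stable tendency. For a mild fall in two phases, the GEE and stratified odds ratios were both 1.04: equally biased, in agreement, and on the opposite side of 1 from the 0.97 that a tendency-driven fall gives. The ratios of later to pre-intervention crossings in the most and least distracted thirds were 0.78 and 1.22 in this case, against 0.82 and 1.20 in the tendency-driven case, so a table of crossings could not tell them apart. In the three-phase version the stratified estimate is the worse of the two (1.04 against 1.02). At 4 crossings with no shift at all, the table gave 0.99 against 1.18, a false alarm.

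**The case for a change.** The best case for acting is that the protocol leaves crossing counts free, no planned analysis holds the participant fixed, and the remedy is cheap: one table and one standard model on existing data, with the primary analysis untouched. If the shift follows stable tendency, the stratified odds ratio recovers the truth. Interval coverage can also suffer. In three-phase runs at an assumed 300 participants it fell to 87–90% with a mild shift and 69% with a strong one; at an assumed 100 it was 93–94% and 86–87%.

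The mechanism, the gap in the planned analyses and the low cost all stand. What does not follow is that the plan needs changing. The coverage losses require a shift for which the documents give no evidence, together with the less favourable working correlation. The protocol follows up both deletion and lapsed recording. The stratified model helps under one form of shift and misleads under another, and the data proposed for choosing between them look nearly the same in both. It also discards participants with no variation in outcome or seen in only one phase: 1–20% at 12 crossings and about 26% at 4.

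**Conclusion.** A baseline-adjusted GEE is a fair choice, and following it as written would still support a sound conclusion. The residual bias is conditional on a change in who crosses. At 12 crossings per phase under independence it is about 3–5% on the odds ratio for a mild shift and 7–9% for a strong one, and roughly half that under an exchangeable correlation. With no shift it is negligible at 12 or more crossings; at about 4 per phase the estimate can fall to 0.96–1.00 even then. The direction follows the shift only if the shift tracks stable tendency.

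These sizes rest on assumed prevalence, between-person spread, crossing counts and shift strength, none of which the documents give beyond the requested weekly minimum. Counting crossings and contributing participants by phase is ordinary descriptive reporting, which an analyst can add without amending the SAP. A participant-stratified model may be shown beside the GEE, but agreement would not rule out bias and disagreement would not identify the correct estimate. No change follows.

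### Does limiting the time-based curiosity check to week 3 of each phase leave the plan with a gap, because it cannot show how the effect changes from week to week?

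*SAP*

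**What the plan says.** The first paragraph of the SAP (Data Analysis) fits logistic GEE models with study phase as the only time variable, "to account for the dependence of crossing events within participants". The covariates are age, race, pre-intervention distraction prevalence and phone type. The reason for the sensitivity analysis is stated: "Given potential for user curiosity at the start of each phase creating changed behavior". The analysis consists of "comparing behavior in the third week of each phase rather than behavior across the full phase".

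The second paragraph raises a related worry, that users "used their phone purposely as they approached the intersection, creating artificial datapoints". The response is not time-based: "we conducted analyses stratified by extent of baseline distraction". The last analysis is a three-way interaction of phase, distraction category and phone type. No week term, phase-by-week interaction or within-phase trend appears.

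The protocol supplies the timing in section IV (Payment), in the reminders to participants. Reminder 2 asks for crossings "at least 4 times a week, and ideally more often". Reminder 4 says "The app will not do anything for several weeks" and that later "they will start getting alerts to remind them not to cross the street while distracted". Neither document gives the length of a phase in weeks.

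**The concern.** The SAP itself suspects behaviour that varies over time within a phase, yet its models cannot trace that behaviour. Testing the alert adds distracted crossings only once alerts are live, so it pushes the intervention OR upward and can mask a benefit. If the full-phase and week-3 ORs differ, a reader will want to know why. Candidate explanations are early testing that stops, an effect that starts late and, if phases run past three weeks, an effect that wears off. Two ORs cannot tell these apart. Stratifying on baseline distraction sorts participants; it does not date the test crossings. Week 3 also discards at least two thirds of the data if crossings are evenly spread. At stake would be the reading of the trial's main result.

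**Working it through.** The documents state no prevalence, effect size, sample size or phase length, so there is no planned figure to reproduce. The inputs below are assumptions, except the 4 crossings a week, which is the minimum in protocol reminder 2: baseline distraction 25% (odds 1/3) in every pre-intervention week, equal crossings per week, phases of equal length, and an undistorted OR of 0.74.

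**1. Is the ambiguity real?** A weekly OR gives probability p = (OR/3)/(1 + OR/3). So p = 0.3023 at OR 1.3, 0.2500 at OR 1.0 and 0.1979 at OR 0.74. The full-phase OR is the odds of the mean weekly p, divided by 1/3.

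| Phase length | Weekly ORs | Mean p | Full-phase OR | Week-3 OR |
|---|---|---|---|---|
| 3 weeks | 1.3 / 0.74 / 0.74 | (0.3023 + 2 × 0.1979)/3 = 0.2327 | 0.910 | 0.74 |
| 3 weeks | 1.0 / 1.0 / 0.74 | (2 × 0.2500 + 0.1979)/3 = 0.2326 | 0.909 | 0.74 |
| 4 weeks | 1.3 / 0.74 / 0.74 / 0.74 | (0.3023 + 3 × 0.1979)/4 = 0.2240 | 0.866 | 0.74 |
| 4 weeks | 0.74 / 0.74 / 0.74 / 1.3 | 0.2240 | 0.866 | 0.74 |

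Yes. Different patterns share a pair of results. The 4-week patterns match at any baseline (0.874 at 10%, 0.858 at 40%), because only the outer weeks are swapped.

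**2. Does the week-3 analysis do its stated job?** The first and third rows are the case the SAP worries about: behaviour distorted at the start, settled afterwards. In week 1 the prevalence rises from 19.8% to 30.2%, which needs alert-testing on (0.3023 − 0.1979)/(1 − 0.1979) = 13% of otherwise undistracted crossings. That moves the full-phase OR from 0.74 to 0.91 (3 weeks) or 0.87 (4 weeks). The week-3 OR stays at 0.74, and the gap between the two signals that something differed outside week 3.

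**3. What is lost if phases last three weeks?** The pair then contrasts weeks 1–2 with week 3. In the 3-week rows the mean p over weeks 1–2 is (3 × 0.2327 − 0.1979)/2 = 0.2501, an OR of 1.00 against 0.74 in week 3. A change from early to late is visible; only the order of weeks 1 and 2 is not. The wearing-off explanation needs phases longer than three weeks, which the documents do not establish.

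**4. What does it cost in precision?** Let n be the week-3 crossings and N the full-phase crossings per participant, ρ the within-phase and c the between-phase correlation, and v(n) = (1 + (n − 1)ρ)/n. On a linear scale the ratio of standard errors is √[(v(n) − c)/(v(N) − c)]. With c = ρ it reduces to √(N/n): √(12/4) = 1.73, √(16/4) = 2.00 and √(24/4) = 2.45 for 3-, 4- and 6-week phases. For 3-week phases with ρ = 0.2 it is √(0.300/0.1667) = 1.34 at c = 0.1 and √(0.400/0.2667) = 1.22 at c = 0.

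**5. Would a weekly model settle the matter?** Not reliably.

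- With three 3-week phases it adds 2 week terms and 4 interaction terms, and reports 6 week-specific ORs, each about as imprecise as week 3.
- If curiosity raises week-1 odds by 1.3 in both the pre-intervention and the intervention phase, every weekly OR is still 0.74 and the interaction is zero; only the weekly prevalences would reveal it.
- Dropping week 1 alone can do worse than week 3: weekly ORs of 1.3/1.0/0.74 give √(1.0 × 0.74) = 0.86, against 0.74.
- Comparing like weeks across phases limits the model to weeks that all phases share. If any phase lasts three weeks, later alert weeks drop out and wearing-off stays unseen.

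**The case for a change.** The strongest argument for the concern is that the SAP raised time-limited behaviour itself, so it should let readers examine it. The week-3 analysis already needs a week-within-phase variable, the data are in hand, and a supplementary phase-by-week model with weekly prevalences would leave both planned estimates untouched. If phases ran well beyond three weeks, week 3 would also say nothing about durability.

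Part of this stands. The plan gives no weekly profile, and two ORs do not identify one. Weekly prevalences would be informative to report, and anyone explaining a gap between the two ORs should be cautious about its cause.

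But the argument is about what else could be learned; it shows no planned estimate to be wrong. Any analysis that reports two summaries leaves the underlying curve unidentified. The patterns in the table were chosen to coincide: they show that ambiguity is possible, not that it is likely or large in this trial. And a weekly pattern could suggest curiosity but not prove it, since it would date a change without isolating the crossings made to test the alert.

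**Conclusion.** The concern does not hold. The SAP promises a comparison free of start-of-phase behaviour and delivers one; it does not promise a description of change over weeks. The absence of a weekly model alters neither the full-phase OR nor the week-3 OR. Alert-testing can bias the full-phase OR (0.74 to 0.91 in the 3-week example), but that is the bias the week-3 analysis is there to expose, and in that example it does.

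This rests on curiosity having faded by week 3, which is the SAP's own premise and cannot be checked from the documents, and on each phase reaching a third week, which the SAP implies. The wider standard error, 1.22 to 1.73 times the full-phase value for 3-week phases under the correlations considered, is a tolerable price for a secondary check beside an unchanged primary analysis. A weekly model is a matter of preference, and the plan needs no correction on this point.

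### Baseline-distraction strata and the pre-intervention reference come from the same crossings, so regression to the mean can pass for effect modification; add a held-out third-week version

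*SAP*

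**What the plan says.** The SAP (Data Analysis, first paragraph) fits GEE logistic models for the association between "study intervention phase (i.e., pre-intervention, intervention, and post-intervention phases) and distraction (whether visual or aural"). On covariates it states: "Models were adjusted for age, race, distraction prevalence during the pre-intervention phase, and type of phone (i.e., Android or iOS"). It recognises early curiosity, giving as its reason: "Given potential for user curiosity at the start of each phase creating changed behavior". The SAP's answer is a restriction by time, described in these words: "a sensitivity analysis was conducted by comparing behavior in the third week of each phase rather than behavior across the full phase".

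The second paragraph gives a further curiosity problem as the reason for stratifying: users "used their phone purposely as they approached the intersection, creating artificial datapoints, we conducted analyses stratified by extent of baseline distraction". It then examines effect modification by pre-intervention distraction and phone type by "including a three-way interaction of intervention phase, distraction category, and phone type", adjusting for age and race.

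Three things are not stated: the cut-points of the distraction category, whether any pre-intervention weeks that define it are kept out of the outcome comparison, and whether the third-week restriction applies to the stratified or three-way models.

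The Protocol (section IV, reminders to participants) asks for crossings "at least 4 times a week, and ideally more often" (item 2). On the start of alerts it says: "We cannot tell them when these alerts will start, and it may be different for different people" (item 4).

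**The concern.** A participant's observed pre-intervention rate is a noisy measure of that person's usual rate. Sorting people on the noisy rate and then measuring change from the same crossings builds a gap into the comparison. People who were low partly by chance appear to rise, and people who were high partly by chance appear to fall. The fall in the high stratum can look like benefit from the alert, and the rise in the low stratum like harm or no benefit. This bears directly on the SAP's judgement of whether effect modification by baseline distraction is meaningful.

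Curiosity is the secondary issue. Stratifying sorts participants and drops no crossings, so the artificial ones remain. If curiosity is greater in the alert phase than before it, the same rate of artificial crossings inflates the OR most where baseline distraction is low. That is the same direction as regression to the mean.

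**Working it through.** The plan gives no rate, effect size, cut-point or sample size for this point, so there is no figure of its own to reproduce.

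**Inputs from the documents.** At least 4 crossings a week are requested (Protocol, section IV, item 2). Phases last at least 3 weeks, because a third week is analysed (SAP). The requested minimum is therefore 4 × 3 = 12 pre-phase crossings. More are likely if phases are longer or people cross more often.

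**Assumed inputs.** Person rates follow Beta(1, 4), with mean 0.20. There is a median split on the observed pre-phase rate, the pre-intervention phase is the reference (the SAP does not name one), and crossings are independent given the person.

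**1. Regression to the mean alone: no effect, no curiosity, 12 crossings.** The chance of x distracted crossings is P(0) = 0.250, P(1) = 0.200, P(2) = 0.157. The mean count is 12 × 0.20 = 2.4. Given x, the expected rate in the next phase is (1 + x)/(5 + 12).

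- Ties at the median placed low (x ≤ 2, 61% of people). Low stratum: mean count (0.200 + 2 × 0.157)/0.607 = 0.847, observed rate 0.847/12 = 0.0706, expected next rate 1.847/17 = 0.1087. OR = (0.1087/0.8913)/(0.0706/0.9294) = 1.60. High stratum: mean count (2.4 − 0.514)/0.393 = 4.8, observed rate 0.40, expected next rate 5.8/17 = 0.341. OR = 0.518/0.667 = 0.78.
- Ties placed high (x ≤ 1 is low). Low: mean count 0.200/0.450 = 0.444, observed rate 0.0370, expected next rate 1.444/17 = 0.0850, OR = 0.0929/0.0385 = 2.41. High: mean count 2.2/0.55 = 4.0, observed rate 0.333, expected next rate 5/17 = 0.294, OR = 0.417/0.500 = 0.83.

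Simulation (600,000 participants, ties low) gives 1.61/0.78 at 12 crossings, 1.33/0.88 at 24 and 1.17/0.94 at 48. Other assumed means (0.30 to 0.50) and between-person spreads at 12 crossings give 1.26 to 2.25 (low) and 0.72 to 0.86 (high) under that tie rule.

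**2. Curiosity alone.** Take a true OR of 0.70 in both strata, with 10% of undistracted crossings turned into distracted ones in week 1 of a 3-week alert phase. At baseline 0.10, p1 = 0.0778/1.0778 = 0.0722. The alert-phase mean is 0.0722 + (0.10/3)(1 − 0.0722) = 0.1031, and OR = (0.1031/0.8969)/(0.10/0.90) = 1.03. At baseline 0.50 the same steps give p1 = 0.4118, mean 0.4314 and OR = 0.76. With the same 10% in pre-phase week 1, the pair becomes 0.77 and 0.71, so most of the gap goes.

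**3. Both together.** Person-level OR 0.70, 3 weeks, 4 crossings a week, ties low. Averaging over people makes the target 0.72/0.73. Entries are low/high ORs.

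| Curiosity by week | Full phase | Week 3, same strata | Week 3, strata from weeks 1-2 |
|---|---|---|---|
| Alert 20/10/0%, none before | 2.75/0.79 | 1.15/0.56 | 0.72/0.73 |
| 10% in week 1 of both phases | 1.28/0.58 | about 1.26/0.58 | 0.72/0.73 |
| Alert 20/10/5%, none before | 3.05/0.84 | 1.89/0.67 | 1.18/0.88 |

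In the second row, dropping the curiosity weeks changes almost nothing, so that gap is regression to the mean. Restriction to week 3 alone does not cure it. Forming strata from other weeks does, because within a stratum the week-3 rates before and during the alert then have the same expectation apart from the effect.

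**4. A different model.** 400 participants, logit-normal rates (mean −1.5, SD 1.0), tertiles, true OR 1, 200 replicates; low/middle/high ORs:

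- no curiosity: full phase 2.94/1.06/0.73; week 3 with held-out strata 1.03/1.01/0.99;
- 30% curiosity in alert week 1: full phase 5.85/1.67/0.95; week 3 with the same strata 2.82/1.05/0.73; full phase with strata from weeks 1-2 4.26/1.67/0.98; both changes together 0.99/1.00/1.00.

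With weekly autocorrelation of 0.5, the combined version gives 1.06/1.03/0.95. With 3% curiosity left in week 3, it gives 1.25/1.13/1.08.

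**5. Phone types within a category.** With true ORs of 0.60 and 0.90 on two platforms sharing one baseline distribution (ratio 0.67), the ratio of ORs was 0.68 in the low stratum and 0.69 in the high stratum. Regression to the mean nearly cancels.

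**The case against.** Stratifying has a defensible purpose: it shows where artificial crossings matter most. A reader might infer that the SAP claims stratifying removes those crossings. It says no such thing, and it handles early curiosity directly with the third-week comparison, which would reveal it in the overall analysis. That stands. What remains is that strata built from the reference data cannot separate curiosity, regression to the mean and a real difference.

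The largest figures use the minimum crossings and the shortest phase. The Protocol has the app inactive for several weeks and kept for the whole semester, so real counts may be higher and the distortion smaller. The tie rule alone moves the low-stratum OR from 1.6 to 2.4. This also stands: the sizes are illustrative.

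Adjustment for pre-phase prevalence does not answer the point. It is stated for the primary models, while the three-way model is described as adjusted for age and race. A person-level covariate also does not undo the overlap between classifying and reference crossings.

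**Conclusion.** The concern holds in a limited form, as an optional improvement. If the category and the reference use the same pre-intervention crossings, regression to the mean pushes the low-baseline OR up and the high-baseline OR down without any true difference. The assumed sizes run from about 1.6/0.8 or 2.4/0.8 at 12 crossings to about 1.2/0.94 at 48. The direction is firm; the size is not.

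Curiosity adds to the gap mainly if it is greater in the alert phase than before it.

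Two stronger readings are not supported. The documents do not show that either distortion occurred: they contain no results, and the SAP calls its evidence of curiosity anecdotal. Nor is the comparison of Android with iOS within a distraction category generally compromised; it is affected mainly if the platforms differ in baseline distraction.

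**What to change.** Keep every existing analysis. Because the SAP describes analyses already conducted, label the additions post hoc.

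1. Add a sensitivity version of the stratified and three-way models that uses the third week of each phase, with the distraction category formed only from the other pre-intervention weeks. Count weeks from each participant's own phase start, since alert start may differ between people.
2. Report the phase-by-category interaction estimate with its CI beside the full-phase result.
3. State that the full-phase stratum differences are open to regression to the mean and to curiosity. Do not read a non-significant held-out interaction as proof of no modification.
4. ORs by week within phase may be shown descriptively.

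The work is a few model runs on crossings already assigned to weeks. Precision falls: with equal crossings per week and equal variance, the SE ratio is √W for a W-week phase, which is 1.73 for 3 weeks, 2.0 for 4 and 2.45 for 6. Three-way cells may be sparse. Strata blur slightly (simulated true mean baseline 0.11 versus 0.32, against 0.11 versus 0.34 using the whole pre-phase, with no pre-phase curiosity). Serial correlation, or curiosity lasting into week 3, leaves some residual bias.
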